3.3 Rational for the Intervention

The pathogenesis of diabetic retinopathy and DMO is complex; inflammation is recognised to play a key role in the series of events that lead to the occurrence and persistence of this sight threatening complication of diabetic retinopathy. Thus, it has been established that early on in the course of the disease there is interaction between circulating immune cells (e.g. monocytes, neutrophils) and the retinal vasculature which begins with leukostasis, which is

accepted as contributory to occlusion, breakdown of the blood retinal barrier (BRB) and subsequent oedema, and degenerative vascular pathology in diabetic retinopathy [8]. Neutrophils and monocytes/macrophages are the major source of pro-inflammatory cytokines, including Vascular Endothelial Growth Factor (VEGF) [9-11]. The increased released of cytokines by inflammatory cells would lead to tissue injury and cell loss [11].

ARA 290 is a synthetic peptide, analogue of erythropoietin (EPO), with marked anti-apoptotic and anti-inflammatory effects [12, 13]. Unlike EPO, ARA 290 is not haematopoietic and, subsequently, is free of the possible side effects linked to EPO such as thrombotic events, which can be life threatening. Given the anti-inflammatory and anti-apoptotic effects of ARA 290 [14, 15], it is possible that this peptide could have a beneficial effect on the treatment of DMO and, thus, warrants investigation [16]. Moreover, ARA 290 protected against retinal blood vessel and neuroglial degeneration and reduced leakage from blood vessels into the retina in an experimental model of diabetic retinopathy [17].

No adverse pharmacologic or toxicologic effects of ARA 290 were identified in general toxicology studies in rats and rabbits after daily subcutaneous administration of up to 6 months duration in rats and 9 months duration in rabbits at maximum doses/concentrations of at least 100 – 1000 fold the initial anticipated minimal effective human dose of 1 microgram/Kg body weight (body surface area adjusted) or the theoretical maximum plasma concentration following bolus administration to the plasma compartment, in standard safety pharmacology battery for central nervous system, respiratory and electrocardiogram effects nor in in-vitro and in-vivo genotoxicity studies [18].

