10.7 Patient Reported Outcomes

Patient reported outcomes will be evaluated by means of EQ-5D 5L and NEI VFQ-25 questionnaires which will be administered to patients at baseline and at week 12 (and at week 16 if applicable). The NEI VFQ-25 is a vision specific patient reported quality of life tool. This validated questionnaire has been used widely to evaluate visual outcomes in patients with eye diseases including DR. In addition to eliciting information about general health and vision it specifically addresses difficulty with near vision, distance vision, driving and the effect of light conditions on vision. This provides a comprehensive evaluation of vision related quality of life. A generic health status measure EQ-5D-5L will be used to generate utility data. Total scores will be recorded and used for the analysis. Suicidal ideation will be assessed using the Columbia Suicide Severity Rating Scale (C-SSRS) which will be administered to patients at baseline and weeks 4, 8 and 12. If at 12 weeks the retina is dry a further visit at week 16 will be arranged and questionnaires completed.

All outcomes will be recorded in CRFs or questionnaires specifically designed for the study.

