10.8 Blood and Urine Sample

A blood sample (34 mls (approximately 2 tablespoons)) and a urine sample will be taken at baseline, 12 weeks (and 16 weeks if the macular oedema resolved at week 12). The urine sample and part of the blood sample will be used to test for the following:

- Pregnancy Test
- Full blood cell count
- CBC with reticulocytes
- HbA1c
- Glucose
- Lipid profile (HDL, LDL, triglycerides)
- C peptide levels
- Creatinine clearance
- Albumin excretion rate
- Liver function test (ALT and AST)

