3.2 Data completion schedule

The following table describes the time points for completion of clinical record forms.

Table 1. Data Completion Schedule

	Screening / Baseline	2 week s	4 weeks	8 weeks	12 weeks	16 weeks*	4 weeks post drug termination**
Consent	✓						
Pregnancy Test	✓						
Medical History	✓		√	√	√	✓	
Medications	✓		√	√	√	✓	
Vital Signs***	✓		√	√	√	√	
Distance Visual Acuity	✓		√	√	✓	√	
Microperimetry	√				✓	√	
Schirmer Test	√				✓	√	
SD-OCT	√		✓	✓	✓	✓	
Wide-angle FFA	✓				✓		
Blood sample for ARA 290 antibodies, immune markers, carbamylated and glycosylated albumin	✓				✓		
Blood sample for full blood cell count	~				√	✓	
Liver function test (LFT)	~				✓	√	
Urine Sample	✓				✓	✓	
Adverse Events		✓	√	✓	✓	√	✓
VFQ-25	~				✓	√	
EQ-5D-5L	~				✓	√	
C-SSRS	~		✓	✓	✓	√	
Telephone check		√					✓

- * 16 week visit will take place only if the retina is found to be dried and the DMO has resolved at week 12
- ** 4 week post study drug termination telephone check will be completed for patients who withdraw from the trial/study drug prior to 12 weeks, or at 12 weeks, and who do not need to attend the 16 week visit.
- *** Vital signs: height (first visit only); weight; heart rate; temperature; blood pressure, oxygen saturation, BMI

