7.4 Trial events

- Change from baseline to week 12 in best corrected distance visual acuity, mean(sd)
- Change from baseline to week 12 in central subfield thickness, mean(sd)
- Change from baseline to week 12 in central retinal sensitivity, mean(sd)
- Change from baseline to week 12 in retinal perfusion, n(%)
- Change from baseline to week 12 Total area of ischaemia, mean (sd)
- Change from baseline to week 12 in tear production, mean(sd) (study eye only)
- Change from baseline to week 12 in patient reported outcomes, mean(sd)
- Change from baseline to week 12 in ARA 290 antibodies, mean(sd)
- Adverse events, n(%)
- % of participants with ≥10 ETDRS letter gain, n(%)
- % of participants with ≥15 ETDRS letter gain, n(%)
- Change from baseline to week 12 in inflammatory biomarkers, mean(sd)
- Change from baseline to week 12 in Carbamylated Albumin, mean(sd)
- Change from baseline to week 12 in Glycosylated Albumin, mean(sd)
- Change from baseline to week 12 in HbA1C, mean(sd)

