	Macular Ischaemia	Present Absent	n(%) n(%)	Present Absent	n(%) n(%)	Extension Reduction	n(%) n(%)	Present Absent	n(%) n(%)	Present Absent	n(%) n(%)	Extension Reduction	n(%) n(%)
		N/A	n(%)	N/A	n(%)	No change	n(%)	N/A	n(%)	N/A	n(%)	No change	n(%)
						N/A	n(%)					N/A	n(%)
	Foveal Ischaemia	Present Absent	n(%) n(%)	Present Absent	n(%) n(%)	Extension Reduction	n(%) n(%)	Present Absent	n(%) n(%)	Present Absent	n(%) n(%)	Extension Reduction	n(%) n(%)
Retinal		N/A	n(%)	N/A	n(%)	No change	n(%)	N/A	n(%)	N/A	n(%)	No change	n(%)
perfusion						N/A	n(%)					N/A	n(%)
	Peripheral Ischaemia	Present Absent	n(%) n(%)	Present Absent	n(%) n(%)	Extension Reduction	n(%) n(%)	Present Absent	n(%) n(%)	Present Absent	n(%) n(%)	Extension Reduction	n(%) n(%)
		N/A	n(%)	N/A	n(%)	No change	n(%)	N/A	n(%)	N/A	n(%)	No change	n(%)
						N/A	n(%)					N/A	n(%)
	Total area of	xx.x ± xx	.x	xx.x ± xx	.x	xx.x ± xx.x		xx.x ± xx	x	xx.x ± xx	.x	xx.x ± xx.x	•
Tear produ	ischaemia iction (mm)*	xx.x ± xx	X	xx.x ± xx	. X	xx.x ± xx.x		_		_		_	
Patient	EQ5d-5L	$xx.x \pm xx$		$xx.x \pm xx$		$XX.X \pm XX.X$		-		-		-	
reported	VFQ-25	$xx.x \pm xx$.x	$xx.x \pm xx$.x	$xx.x \pm xx.x$		-		-		-	

Northern Ireland Clinical Trials Unit

outcome scores C-SSR	xx.x ± xx.x	$xx.x \pm xx.x$	xx.x ± xx.x	-	-	-
% of participants with ≥ 10 ETDRS letter gain	· -	-	n(%)	-	-	n(%)
% of participants with ≥ 15 ETDRS letter gain		-	n(%)	-	-	n(%)

^{*}Study eye only

Mean ±SD presented for continuous variables (or median [interquartile range] when appropriate) and no. (%) for categorical variables.

Table 3.2 Descriptive Statistics for Serum for ARA 290 Antibodies

Status	Timepoint	Result	n =
Screening Status	Baseline	Negative	N (%)
		Potential Positive	N (%)
	Week 12	Negative	N (%)
		Potential Positive	N (%)
Confirmatory Status	Baseline	Not Applicable	N (%)
		Negative	N (%)
		Positive	N (%)
	Week 12	Not Applicable	N (%)
		Negative	N (%)
		Positive	N (%)

Table 3.3 Exploratory Analysis (Non-Study Eye subgroups)

		Non-Study Eye (Central subfield thickness <400 microns)				Non-Study Eye(Central subfield thickness ≥400 microns)							
		Baseline		Week 12 Change		је	Baseline		Week 12		Change		
		n = ((%)	n = ((%)	n = (°	%)	n = ((%)	n = ((%)	n =	(%)
Primary outcome; best corrected distance visual acuity		$xx.x \pm xx.x$ $xx.x \pm xx.x$.X	xx.x ± xx.x		xx.x ± xx.x		xx.x ± xx.x		xx.x ± xx.x		
Central sub thickness (xx.x ± xx.x		xx.x ± xx.x		xx.x ± xx.x		xx.x ± xx.x		xx.x ± xx.x		xx.x ± xx.x	

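### The SAP summarises the C-SSRS only as a continuous score at baseline and week 12, so the week 4 and 8 suicidality assessments have no output of their own; collected blood counts and reticulocytes have none either

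*SAP*

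**What the plan says.** **C-SSRS collection.** Protocol section 10.7 introduces the C-SSRS as the assessment of suicidal ideation, "which will be administered to patients at baseline and weeks 4, 8 and 12". The protocol's schedule of assessments and the SAP's data completion schedule (section 3.2) show the same visits, and the SAP's definition of terms (section 4) repeats them. A week 16 assessment was conditional on a dry retina, and SAP section 6 states that no patient needed that visit.

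**C-SSRS output.** There is one row in SAP Table 3.1, "outcome scores C-SSR", under patient reported outcome scores. It has mean ± SD placeholders for baseline, week 12 and change. The table footnote reads "Mean ±SD presented for continuous variables (or median [interquartile range] when appropriate) and no. (%) for categorical variables". SAP section 7.4 does not name the C-SSRS; the matching line is "Change from baseline to week 12 in patient reported outcomes, mean(sd". SAP section 7.5 and Tables 4.1 and 4.2 cover adverse events and deaths, with no C-SSRS row. The data listings promised are for characteristics, visual outcomes and adverse events.

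**Haematology.** Protocol section 10.8 lists a full blood count and "CBC with reticulocytes". SAP section 3.2 schedules "Blood sample for full blood cell count" at baseline and week 12 (and week 16 where applicable). No blood count or reticulocyte item appears in SAP sections 7.2 to 7.5 or in Tables 1 to 5. Protocol section 3.3 gives as part of the drug's rationale: "Unlike EPO, ARA 290 is not haematopoietic".

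**The concern.** Suicidal ideation is a safety finding. What matters is whether any patient had it on treatment, when, and whether it was worse than at entry. A group mean or median at week 12 answers none of these, and it leaves out two of the three on-treatment visits at which the question was asked. The summary also has no stated meaning. Protocol section 10.7 names the EQ-5D-5L and NEI VFQ-25 as the patient reported outcomes, with total scores used for analysis, and brings in the C-SSRS afterwards without a scoring rule.

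Further information on safety is a stated purpose of the study (protocol section 12.1, SAP section 5). Protocol section 3.3 says that treatment is being extended for the first time to 84 days, from the 28 days used in most previous studies, and section 4.2 says that the data will inform larger trials. With ten patients, a single case is a material result. Read alone, Table 3.1 could suggest no change in suicidality when a patient had reported ideation during treatment.

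The blood counts raise a similar but smaller issue. The trial collects data bearing on whether this erythropoietin analogue affects red cell production, and plans no display of them.

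**Working it through.** The plan states no alpha, power or effect size for its ten patients and describes the analysis as descriptive, so there is no figure of its own to reproduce. The check compares what is collected with what is tabulated.

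**1. C-SSRS assessments with a planned cell.** Inputs: 10 patients (SAP section 5); on-treatment visits at weeks 4, 8 and 12 (protocol section 10.7).

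- Scheduled on treatment: 10 × 3 = 30.
- Tabulated in Table 3.1 (week 12 only): 10 × 1 = 10.
- With no cell or listing of their own: 30 − 10 = 20, and 20/30 = 67%.

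**2. What the planned summary shows.** The documents give no coding, so assume 0 = no ideation or behaviour and 1 = any. For k positives among 10 at one visit, mean = k/10 and SD = √[(k/10)(1 − k/10)(10/9)].

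| Situation | Week 12 mean ± SD | Week 12 median [IQR] |
|---|---|---|
| One patient positive at week 4 or 8 only, all other assessments negative | 0.0 ± 0.0 | 0 [0, 0] |
| One positive at week 12 | 0.1 ± 0.32 | 0 [0, 0] |
| Two positive at week 12 | 0.2 ± 0.42 | 0 [0, 0] |

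In the first row the change from baseline is also 0.0. The median alternative does not help: it hides one or even two positives out of ten at week 12 itself.

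**3. What an any-visit count shows.** For the first row the result is 1/10 = 10%. The exact (Clopper–Pearson) 95% limits are:

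- lower: 1 − 0.975^(1/10) = 0.0025, or 0.3%;
- upper: the p solving (1 − p)^10 + 10p(1 − p)^9 = 0.025, which is p = 0.445, or 44.5%.

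Even a fully tabulated 0/10 leaves a one-sided 95% upper limit of 1 − 0.05^(1/10) = 25.9%. The individual listing therefore matters as much as the percentage.

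**4. Haematology.** Scheduled time points: 2 (baseline and week 12). Planned rows: 0. From the same list of tests, HbA1c, glucose, lipids, C peptide and AST/ALT all reach SAP Table 1 with a week 12 column.

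**5. The adverse event route.** Protocol section 13.2 has patients asked about adverse events at each visit after treatment starts, which includes weeks 4 and 8. Section 13.8 puts all of them on the CRF form. SAP Table 4.1 has rows for psychiatric disorders and for investigations, for both AEs and SAEs. Table 4.2 has a row for abnormal blood test results, and an adverse event listing is planned. Neither document says that a positive C-SSRS answer or an out-of-range count must be recorded as an adverse event. The only psychiatric term in the Table 4.2 shell is insomnia, and Table 4.1 has no blood and lymphatic class.

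**The case against.** A reader might infer that ideation at week 4 or 8, or any haematological effect, could not appear in the planned tables at all. The documents do not support that. The adverse event route is real and covers every visit, and an event recorded there would be both counted and listed. What remains is that the route depends on a separate act of recording that the documents do not require for a C-SSRS answer or a blood count. A within-range shift in haemoglobin or reticulocytes would not be expected to pass through it.

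The DMEC reviews safety data about every four weeks and a full report about every three months (protocol section 15.3). Oversight during the trial therefore does not hang on Table 3.1. This stands, but it does not repair the final report.

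The 1/10 example is hypothetical and rests on an assumed coding. That is correct: nothing in the documents says that any patient had ideation, and the example shows only how the table would behave.

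The absence of a haematopoietic effect is background rationale and not an objective or outcome, and ten uncontrolled patients could not establish it. This also stands. It makes the haematology gap a lesser matter of unreported safety data and not a failure to meet a stated aim.

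**Conclusion.** The point holds in this form. The C-SSRS is planned only as an undefined continuous score at baseline, week 12 and change. Of 30 scheduled on-treatment assessments, 20 have no summary or listing of their own and would surface only through separate adverse event recording. That is a poor summary of a safety classification, and it is worth correcting because it limits what the safety report can conclude. The count of 20 assumes ten patients attending all visits; the numerical illustration assumes 0/1 coding and no other positive assessments.

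The haematology gap is secondary. Blood count and reticulocyte data are collected at two time points and appear in no planned table. Abnormal values would show only if recorded as adverse events. It does not follow that the trial was meant to prove, or could prove, that the drug has no haematopoietic effect.

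**What to change.** **C-SSRS.** Remove the row from Table 3.1 and place it in the safety output. Replace the mean ± SD (and median [IQR]) with:

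- n (%) with any post-baseline ideation or behaviour, at each of weeks 4, 8 and 12 and at any of them;
- n (%) worse than baseline;
- a patient listing of responses by visit.

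The SAP should state which C-SSRS responses count as ideation or behaviour, and what counts as worse than baseline.

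**Haematology.** Add the blood count and reticulocyte values held on the CRF to the tables: baseline, week 12, paired change, and number outside the reference range. The CRF is not reproduced in the documents, so the analytes should be taken from it.

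**Cost.** One or two table shells and a listing. The assessments and samples are already scheduled, so no new visits or tests are needed.

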9.5 Study Drug Administration

After giving consent and being recruited on to the study, the patient's baseline assessment will be carried out and recorded.

The first subcutaneous injection of ARA 290 at a dose of 4 mg will be self-administered by the patient at the first patient visit. The patient will receive practical instructions on how to self-administer the drug. The patient will be required to remain at the site for one hour after the first administration for observation. Any adverse events will be recorded in the CRF. The patient will self-administer subsequent 4 mg subcutaneous injections for the 84 day study drug period unless there is reason for discontinuation of the study drug.

Study medications should be injected subcutaneously in the front or side of the thigh daily, in the morning. Patients are advised to rotate daily injection sites to avoid injecting into the same area repeatedly. In the unlikely event that the patient is unable to inject into the thigh they may inject into the abdomen.

The patient will be provided with Study Drug Administration Guidelines to instruct them how to reconstitute the study drug for injection and how to administer the injection. The patient will also be provided with a Study Drug Diary Card and will be instructed to note each daily study drug administered.

The PI or designee should confirm that all study drugs are administered as per protocol by checking the returned Study Drug Diary Card. Any anomalies in study drug used/unused will be queried with the patient and in the event that the patient has not administered study drug, this will be recorded as a protocol deviation in the CRF.

The completed Study Drug Diary Card should be filed alongside the patient CRF.

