9.6 Study Drug Termination

The study drug will be discontinued if any of the following conditions are met prior to the study drug treatment period of 12 weeks:

- 1. Patient or clinician request for withdrawal from the study.
- 2. Patients whose sight is determined as deteriorating to the point of a 10 letter drop in sight. The study drug will be stopped and the patient will be offered the current standard care treatment.

Whilst on the study enrolled participants, [i.e. patients with DMO and thick retinas (400 microns or more)] will be receiving the study drug rather than the current standard treatment (currently anti VEGF drugs in the NHS). Patients who wish to withdraw from the study, those in whom sight loss occurs during the duration of the study or those completing the study in who DMO persists, will be offered this standard care treatment.

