10.10 Telephone Checks

The PI or designee will contact the patient by telephone 2 weeks post enrolment onto the study to check compliance with study drug administration and to assess if the patient is experiencing any adverse events.

For those patients who withdraw from the trial/study drug prior to 12 weeks or following the completion of 12 weeks of treatment (and who do not need to attend the 16 week visit), the PI or designee will contact the patient by telephone 4 weeks post study drug termination to assess if the patient is experiencing any adverse events.

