13.7 Adverse Event Reporting Period

The AE reporting period for the trial begins upon enrolment into the trial and ends 30 days following the last administration of the study drug. All AEs assessed by the PI as possibly, probably or definitely related to the study drug and all SAEs that occur during this time will be followed until they are resolved or are clearly determined to be due to a patient's stable or chronic condition or intercurrent illness(es).

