5. SAMPLE SIZE CALCULATIONS

This will be an early phase, open label, interventional pilot study to evaluate the potential beneficial effect of ARA 290 for the treatment of patients with DR and DMO and further assess the safety of this treatment. Ten patients will be recruited. A sample of this size is expected to be sufficient to provide an indication of a potential beneficial effect of the drug on the outcomes investigated and further information on safety of ARA 290 in a diabetic population. Data obtained in this study will be used to inform future larger studies.

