6. ANALYSIS PRINCIPLES

In participants in whom both eyes are eligible for inclusion into the study, the eye with the better BCVA will be used as the study eye; however data will be collected and evaluated for both eyes.

Descriptive statistics will be used for the evaluation of primary and secondary outcomes. Differences in mean (SD) change from baseline for all the continuous variables investigated including visual acuity, central subfield thickness, area of retinal ischaemia, retinal sensitivity, patient reported outcome scores as well as levels of ARA 290 antibodies. Confidence intervals will also be presented. When data is not normally distributed, median (interquartile range) will be presented.

Adverse events will be presented using counts and percentages. Additionally, the % of participants with 10 or more and 15 or more ETDRS letter gain will be also reported. Data obtained at week 16 would have been similarly evaluated; however no patients required a 16-week visit.

Exploratory analysis in relation to inflammatory markers and carbamylated and glycosylated albumin will also be observed from baseline to the week 12 visit.

If the retinal perfusion image analysis is not available, it may be presented in a later report.

Additional analysis (not specified in the protocol) will be performed to explore the treatment effect in the non-study eye for (a) those patients with DMO in the non-study eye that did not fulfil the criteria for inclusion into the study (e.g. in patients with central retinal subfield thickness of < 400 microns or in patients with non-central involving DMO) and (b) patients with DMO in the non-study eye that fulfilled criteria for inclusion into the study (e.g. ≥ 400 microns).

As the analysis is only descriptive, no imputation or sensitivity analysis will be performed.

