7.3 Trial treatment

- Number of treatments administered
- Treatment compliance/tolerance including reasons for early discontinuation or protocol violations, n (%)
- Additional treatments given

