Mean ±SD presented for continuous variables (or median [interquartile range] when appropriate) and no. (%) for categorical variables.

Data listings for the visual outcomes will be included as an appendix in the final statistical report.

Table 3.4 Exploratory Analysis (All Eyes with DMO >400 Microns)

		All Eyes with DMO ≥ 400 Microns						
		Baseline		Week	(12	Chang	је	
		n = (%)		n = ((%)	n = (%)		
Primary outcome; best corrected distance visual acuity		xx.x ± xx.x		xx.x ± xx.x		xx.x ± xx.x		
Central sub thickness (r		xx.x ± xx	.x	xx.x ± xx.x		xx.x ± xx.x		
Central reti (dB)	nal sensitivity	xx.x ± xx	.x	xx.x ± xx.x		xx.x ± xx.x		
	Macular Ischaemia	Present Absent N/A	n(%) n(%) n(%)	Present Absent N/A	n(%) n(%) n(%)	Extension Reduction No change N/A	n(%) n(%) n(%) n(%)	
Retinal perfusion	Foveal Ischaemia	Present Absent N/A	n(%) n(%) n(%)	Present Absent N/A	n(%) n(%) n(%)	Extension Reduction No change N/A	n(%) n(%) n(%) n(%)	
	Peripheral Ischameia	Present Absent N/A	n(%) n(%) n(%)	Present Absent N/A	n(%) n(%) n(%)	Extension Reduction No change N/A	n(%) n(%) n(%) n(%)	
	Total area of ischaemia	xx.x ± xx.x		xx.x ± xx.x		xx.x ± xx.x		
% of participants with ≥ 10 ETDRS letter gain		-		-		n(%)		
% of partic	ipants with ≥ RS letter gain	-		-		n(%)		

Table 4.1 Safety Outcomes

		ARA290 n= <n></n>
AEs,	Total number of Adverse Events (AEs)	n
SAEs	Number of patients experiencing an AE	n (%)
and	Total number of Adverse Reactions (ARs)	n
SUSARs	Total number of Serious Adverse Events (SAEs)	n
	Number of patients experiencing an SAE	n (%)
	Total number of Serious Adverse Reactions (SARs)	n
	Total number of events related to study drug and unexpected (SUSARs)	n
	Total number of Deaths	n (%)
AE	General disorders and administration site conditions	n (%)
	Vascular disorders	n (%)
	Eye disorders	n (%)
	Gastrointestinal disorders	n (%)
	Psychiatric disorders	n (%)
	Metabolism and nutrition disorders	n (%)
	Infections and infestations	n (%)
	Nervous system disorders	n (%)
	Musculoskeletal and connective tissue disorders	n (%)
	Injury, poisoning and procedural complications	n (%)
	Respiratory, thoracic and mediastinal disorders	n (%)
	Skin and subcutaneous tissue disorders	n (%)
	Immune system disorders	n (%)
	Renal and urinary disorders	n (%)
	Cardiac disorders	n (%)
	Ear and labyrinth disorders	n (%)
	Investigations	n (%)
SAE	General disorders and administration site conditions	n (%)
	Vascular disorders	n (%)
	Eye disorders	n (%)
	Gastrointestinal disorders	n (%)

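### SAP Tables 4.1 and 4.2 pool all-cause events on ARA 290 with events up to 30 days after the last dose, when anti-VEGF is offered, and for completers no scheduled contact records its start

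*SAP*

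**What the plan says.** **Safety tables.** Table 4.1 in SAP Appendix 1 has one column, headed ARA290. Its all-cause rows ("Number of patients experiencing an AE", total AEs and SAEs, and AEs and SAEs by organ class) stand next to counts of ARs, SARs and SUSARs. Table 4.2 lists organ classes and preferred terms in three columns: Total, AR and UAR. No table or SAP text divides events at the last dose or at the start of another treatment.

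**Reporting window.** The AE period opens at enrolment and "ends 30 days following the last administration of the study drug" (Protocol 13.7). Protocol 13.1 defines an AE irrespective of cause, and 13.8 brings all of them into the safety analysis. Patients self-inject "for the 84 day study drug period" (Protocol 9.5).

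**Change of treatment.** Protocol 8.4 returns early stoppers to standard care, which it identifies as anti-VEGF. Protocol 9.6 adds that "those completing the study in who DMO persists, will be offered this standard care treatment". The week-16 visit is reserved for patients whose oedema has resolved at week 12 (footnote to Protocol Table 2 and SAP Table 1). SAP section 6 reports on that visit: "however no patients required a 16-week visit".

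**Records after the last dose.** Protocol 10.10 schedules a call "4 weeks post study drug termination to assess if the patient is experiencing any adverse events". In both schedules the column for that contact is ticked for adverse events and the telephone check, but not for Medications. SAP 7.3 lists "Additional treatments given" as an output, but the Table 2 shell in Appendix 1 has no row for it.

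**The concern.** Further safety information is a stated purpose of the study (Protocol 12.1), and Protocol 3.3 says that treatment is being extended from 28 to 84 days for the first time. There is no control arm, so the AE tables are the safety result, and nothing beside them shows what the change of treatment contributes.

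Patients enter untreated for DMO, so any anti-VEGF injection given after the study drug would be their first. Protocol 3.2 names complications of such injections, which it calls infrequent: endophthalmitis, retinal detachment, cataract and raised eye pressure. Table 4.2 already has rows for a drop in visual acuity and for flashing lights. From the planned tables a reader could not tell whether such an event arose on ARA 290, after it was stopped, or after a first injection.

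The causality scale in Protocol 13.4 asks whether something else explains the event. For completers, the most foreseeable other explanation is not something that any scheduled contact in the window records.

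**Working it through.** The documents give no AE rates, and the sample size ("Ten patients will be recruited") comes without a calculation, so there is no stated figure to reproduce. The check is mainly a reading of the sections against each other, with some arithmetic for scale.

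**1. Can the change of treatment fall inside the AE window?** Early stoppers are offered anti-VEGF on stopping. For completers, the week-16 visit requires resolved oedema and nobody needed that visit, so no completer met the condition. All completers therefore fall under the offer in Protocol 9.6. Protocol 10.9 equates study completion with week 12, and the AE window stays open for 30 days after the last dose. The offer can therefore fall inside the window. Its date is not stated.

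**2. Which figures pool the two periods?**

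| Output | Basis | Split by period? |
|---|---|---|
| Table 4.1: AE, SAE and organ-class rows | all causes | no |
| Table 4.2: Total column | all causes | no |
| Table 4.1: AR, SAR, SUSAR rows; Table 4.2: AR, UAR columns | filtered by causality | no, but restricted to events rated at least possibly related |

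**3. What is scheduled after the last dose?**
- *Completers:* the 4-week call only, without Medications. It falls at day 28, so the last 30 − 28 = 2 days of the window have no scheduled contact.
- *Early leavers:* the same call, plus a week-12-type evaluation (Protocol 10.9), which includes Medications. Its timing relative to anti-VEGF is not stated.

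**4. Post-drug share of the time from first dose.** Share = 30 / (days on drug + 30).
- Completer, 84 days: 30 / 114 = 26.3%.
- Stop at day 56: 30 / 86 = 34.9%. Stop at day 28: 30 / 58 = 51.7%.
- The footnote to SAP Table 2 expects 120 doses in 120 days, which would give 30 / 150 = 20%. The two treatment periods need to be reconciled.

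These are shares of time, not of events.

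**5. What one patient can do.** With 10 patients, one is 1/10 = 10 percentage points. That applies only to rows that are percentages of patients, and only if the patient had no earlier event in the row. Rows that are plain event counts have no percentage, and someone already counted on drug adds nothing later to a patient-level row.

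**6. Illustration under assumed rates.** Let *q* be each patient's chance of an AE of any cause after the change of treatment, and *p* the chance of at least one AE on drug. Assume that all ten change treatment and that the two periods are independent. Then P(at least one such patient) = 1 − (1 − *q*)^10, and the patients-with-AE row becomes *p* + (1 − *p*)*q*.

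| *q* (assumed) | P(at least 1 of 10) | Row at *p* = 50% (assumed) | Increase, points |
|---|---|---|---|
| 5% | 40% | 52.5% | 2.5 |
| 10% | 65% | 55% | 5 |
| 20% | 89% | 60% | 10 |
| 30% | 97% | 65% | 15 |

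Over *p* = 30% to 70% and the same *q*, the increase (1 − *p*)*q* runs from 1.5 to 21 points. This shows the effect of pooling later follow-up, not of anti-VEGF itself, and none of the rates comes from the documents.

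**The case against.** A reader might infer that anti-VEGF events would be counted as effects of ARA 290. The documents do not support that. An AE is defined without regard to cause, and attribution rests on the AR, SAR, UAR and SUSAR figures, which need an assessed relation to study drug. Table 4.2 gives every organ class and preferred term its own AR and UAR columns. The assessor is a retinal specialist at the single site and may well know that an injection was given.

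Two further inferences also go too far:
- *That every completer received anti-VEGF within the window.* The treatment is offered; no offer date, uptake or first-injection date is given. Protocol 16.11 places the return to standard care after the trial, without a date per patient.
- *That the 4-week call is the only contact after the change for everyone.* Early leavers have the evaluation in Protocol 10.9. Patients may also report events themselves, and SAE follow-up forms describe how the event was treated.

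It can also be said that a 30-day follow-up rightly captures delayed drug effects, that AE listings are planned, and that in ten patients listings can show each case.

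Most of this stands, and it limits the point to the all-cause figures. It does not remove it. The causality filter does nothing for the all-cause rows and, for completers, works without a scheduled record of the competing treatment. The listings' columns are not specified, so they do not promise onset relative to last dose or to anti-VEGF. Delayed effects remain visible in a separate post-drug column.

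**Conclusion.** The point holds for the all-cause AE, SAE and organ-class rows of Table 4.1 and the Total column of Table 4.2. They pool on-drug events with up to 30 days of later events, in a period when a change to anti-VEGF is foreseen and, for completers, no scheduled contact records its start.

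Contamination is foreseeable but not shown: between 0 and 10 patients could be affected. The 26% is the post-drug part of a completer's 84 + 30 days, an upper bound on the share of that time spent under anti-VEGF, and says nothing about how far any AE figure is raised. A shift of 10 points per patient is possible only under the conditions in step 5 of the working.

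The conclusion assumes that SAP section 6 covers all completers and that the week-16 rule was applied as written. It is a cheap improvement to the reporting of an uncontrolled ten-patient study, and does not make the planned tables invalid.

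**What to change.** 1. In Table 4.1 (all-cause rows) and Table 4.2 (Total column), report events with onset up to the last dose separately from events after it, using each patient's actual last-dose date.
2. In the tables and the AE listings, flag events with onset on or after the first standard-care DMO treatment, and give onset relative to last dose in the listings.
3. Record DMO treatment, eye and date at the 4-week call. SAP section 6 suggests that week-12 visits were already over when it was written; if the calls are complete, retrieve these items from the single centre's notes.
4. Add the additional-treatments row that SAP 7.3 promises to the SAP Table 2 shell.
5. Reconcile the 84-day period in Protocol 9.5 with the 120-dose, 120-day footnote to SAP Table 2.

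The cost is extra columns in existing shells, a flag, and one question in a planned call or a notes check for at most ten patients. The downside is smaller counts per column.
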